3.7 Safety Monitoring Committee

The SMC is composed of the sponsor's Medical Monitor and an independent Medical Monitor and will review the safety data (e.g., AE listings, laboratory data, vital sign data, trough levels) biweekly during Segments 1 and 2, as data become available. Formal meetings of the SMC will be convened if warranted based on data obtained at any time during Segments 1 and 2. Any AEs will be discussed between SMC members in an ongoing basis. The SMC will continue to review the safety data periodically during Segment 3.

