	
(FVC), forced expiratory volume in 1 second (FEV1), peak expiratory flow (PEF), and FEV1/FVC ratio.
 
 • Clinical Global Impression scales • Quality of life assessment

Safety Assessments
	
Physical examinations, vital signs, and clinical laboratory tests will be assessed at each study visit.
 
Virology will be assessed at Screening, Baseline, and every 12 weeks during dosing and at Study Discontinuation which is 30 days after the final dose of the IMP. An archive sample for virology will be taken at Baseline.
 
Immunogenicity testing will be assessed at Screening and every 4 weeks during Segment 2, every 12 weeks during Segment 3 and at Study Discontinuation which is 30 days after the final dose of the IMP.
 
At each IMP infusion during Segments 1 and 2 Study Visits, the study personnel will assess AEs and vital signs. Subjects will be provided a diary to record AEs and infusions between visits.
 
All treatment-emergent AEs and SAEs will be documented, including assessments of their severity and relatedness to the IMP.
 
Laboratory abnormalities, physical examination findings, and vital sign abnormalities that are clinically significant, as judged by the investigator, will be reported as AEs.

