- b. Weeks 2, 6 and 10 visits may be performed at subject's home by a home health nurse or at an ancillary site in lieu of the study site.
- c. The Week 12 visit is the end of treatment in Segment 2. Subjects are asked to Segment 3 based on Investigator's and Sponsor's decision. Subjects who discontinue the study during Segment 2 are required to undergo these assessments as well, except IMP infusion.
- d. Women with child-bearing potential only.
- e. Genetic test for hypoplasminogenemia is optional. Subjects who already have known test results or who do not wish to participate can omit the test.
- f. See Section 3.5.2.6 for PK sampling time points.
- g. The types and timing of clinical assessments depend on each subject's disease presentation and include but are not limited to: 1) measurement of visible lesions using photographs, 2) functionality tests (e.g., spirometry), 3) imaging of non-visible lesions (e.g., ureteral, oropharyngeal and bronchial) based on the investigator's discretion. See Section 3.5.2.13 for details.
- h. Vital signs are taken within 15 minutes before and 15 minutes after each infusion that takes place at the study site and when a home health nurse is present during a visit.
 - i. At each study visit, the IMP is infused by study staff on site. Between study visits, the IMP is infused at the site or an ancillary site, or at home by a home health nurse or self-administered by the subject or a caregiver. See Section 3.2 for details. Subjects' infusions window for both Segment 2 and Segment 3 is +/- 1 day.
- j. For subjects who participate in Segment 1, these baseline assessments are performed on Day -4 only. For subjects who do not participate in Segment 1 and are directly entering Segment 2, these baseline assessments

are performed on Day 0 only. Any of these assessments that have already been performed at Screening within the past 7 days may be omitted.

- k. A pre-infusion sample for PK profile is required for subjects in Segment 1 only (i.e., the 96-hour time point). Subjects directly entering Segment 2 do not require PK profile.
- l. Visit windows for Segment 2 are +/- 1 day and for Segment 3 are +/- 7 days. Visit windows for the Safety Follow-up, 30 days post final dose, are +/- 3 days.
- m. A chest X-ray will be performed at baseline and Week 12 at the investigator's discretion.
- n. The Clinical Global Impression and Quality of life assessment will be performed at the Week 48 Visit only in Segment 3.

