- AE assessment
- Provision of subject diary and instructions

For subjects entering Segment 2 after completing Segment 1, Baseline assessments are not needed. Instead, the following procedures will be conducted:

- Prior to IMP infusion, blood samples for trough plasminogen activity, antigen, and D-dimer (i.e., the 72-hour sample after first dose)
- Vital signs (before and 15 minutes after infusion)
- IMP infusion
- Concomitant medications
- AE assessment
- Provision of subject diary and instructions

3.5.1.6 **Segment 2, Week 2, Week 6, Week 10**

These visits will occur either at the study site or ancillary site, or at the subject's home by a home health nurse (US subjects only).

- Prior to IMP infusion, blood samples for trough plasminogen activity, antigen, and D-dimer
- Vital signs (before and 15 minutes after infusion)

- IMP infusion

3.5.1.7 **Segment 2, Weeks 4 and 8**

- Clinical assessments (Section 3.5.2.13)
 - Measurements and photographs of visible lesions
 - Imaging of non-visible lesions
 - Functionality testing
- Clinical Global Impression
- Quality of life assessment
- Urine pregnancy test (women of childbearing potential)
- Prior to IMP infusion, blood and urine samples for clinical laboratory tests (hematology, biochemistry, urinalysis, fibrinolysis panel, coagulation panel)
- Prior to IMP infusion, a blood sample for anti-plasminogen antibody
- Prior to IMP infusion, blood samples for trough plasminogen activity, antigen, and D-dimer
- Vital signs (before and 15 minutes after infusion)
- IMP infusion
- Concomitant medications
- AE assessment
- Review and provision of subject diary

3.5.1.8 **Segment 2, Week 12 or Discontinuation**

The following assessments will be conducted at the study site at Week 12 or at the final visit if a subject discontinues treatment:

- Weight
- Physical examination
- Urine pregnancy test (women of childbearing potential)
- Clinical assessments (Section 3.5.2.13)
 - Measurements and photographs of visible lesions
 - Imaging of non-visible lesions
 - Functionality testing
- Clinical Global Impression
- Quality of life assessment

- Chest X-ray, at the investigator's discretion
- Prior to IMP infusion, blood and urine samples for clinical laboratory tests (hematology, biochemistry, urinalysis, fibrinolysis panel, coagulation panel)
- Prior to IMP infusion, blood samples for virology (serology and PCR) testing
- Prior to IMP infusion, a blood sample for anti-plasminogen antibody

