5.2 Eliciting and Reporting Adverse Events

The condition of the patient will be monitored throughout the study. At each visit, AEs will be elicited using a standard non-leading question such as “*How have you been since the last visit / during the previous study period?*” AEs will also be elicited through the use of Subject Diary cards, which the investigator will review in detail with the subject at each visit, ensuring accuracy and completeness of entries recorded by the subject.

Any AE or ADR occurring during the study will be noted in detail on the appropriate pages of the eCRF. If the patient reports several signs or symptoms, which represent a single syndrome or diagnosis, the latter should be recorded in the eCRF. The investigator will grade the severity of all AEs or ADRs (mild, moderate or severe), the seriousness (non-serious or serious) and relatedness, as defined in Section 5.1.

In the event of clinically significant abnormal laboratory findings, the tests will be repeated and followed-up, as needed. Diseases, signs and symptoms, and/or laboratory abnormalities already existing before the first administration of IMP are not considered as AEs when observed at a later stage unless they represent a worsening.

The investigator should always provide detailed information concerning any abnormalities and the nature of, and reasons for any necessary action(s), as well as any other observations or comments, which are useful for the interpretation and understanding of the subjects’ AEs or ADRs.

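### AE elicitation and diary review are required at each visit, but the schedule and Section 3.5.1.6 omit both at Weeks 2, 6 and 10, leaving 28 days between a subject's AE questions in Segment 2

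*Protocol*

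**What the plan says.** Section 5.2 of the protocol sets a general rule: "At each visit, AEs will be elicited using a standard non-leading question". It adds that the investigator goes through the diary with the subject at each visit. The opening paragraph of Section 5 repeats the elicitation rule. Sections 3.5.2.12 and 3.9 have study personnel review the diary at each visit.

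Section 3.5.1.6 covers Weeks 2, 6 and 10. It begins "These visits will occur either at the study site or ancillary site" and lists three tasks: trough samples, vital signs and infusion of the investigational product. Table 2 matches it: vital signs and infusion are marked in those columns, while AE assessment, concomitant medications and subject diary are blank. Footnote b of Table 2 also uses the word visit: "Weeks 2, 6 and 10 visits may be performed at subject's home by a home health nurse or at an ancillary site".

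Section 3.7 says the SMC "will review the safety data (e.g., AE listings, laboratory data, vital sign data, trough levels) biweekly during Segments 1 and 2", as the data come in. It adds: "Any AEs will be discussed between SMC members in an ongoing basis".

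**The concern.** Someone performing the Week 2, 6 or 10 visit cannot follow both instructions. The general rule calls for the AE question and a diary check; the visit list and schedule call for neither. Staff usually work from the visit list, so the likely reading is that AEs are not asked about, even though a nurse or staff member is there and an infusion is being given.

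Two things are at stake. First, the SMC's review is meant to combine AE listings with vital signs and trough levels. Weeks 2, 6 and 10 supply the last two for a subject but schedule nothing for the first. Second, safety over 48 weeks is a secondary objective (Section 2.2) and treatment-emergent AEs are to be summarized (Section 6.3.4). If some personnel follow Section 5 and others follow Table 2, Segment 2 events are collected on two different schedules, and a pooled table will not show it.

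**Working it through.** The plan states no figure for the frequency of AE elicitation, so the check is a comparison of passages and a count.

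**1. Passages side by side (Segment 2, after Day 0)**

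| Task | Weeks 2, 6, 10 (3.5.1.6, Table 2) | Weeks 4, 8, 12 (3.5.1.7, 3.5.1.8, Table 2) | General rule |
|---|---|---|---|
| Trough sample, vital signs, infusion | scheduled | scheduled | – |
| AE assessment | not scheduled | scheduled | each visit (5, 5.2) |
| Diary review | not scheduled | scheduled | each visit (3.5.2.12, 3.9, 5.2) |
| Concomitant medications | not scheduled | scheduled | no each-visit rule found |

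The visit list and the table agree with each other, so this is not a single missed cell. The conflict concerns AE assessment and the diary. Concomitant medications are missing from the same visits but contradict no other section.

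**2. Share of visits without an AE question, per subject**
- Visits after Day 0: Weeks 2, 4, 6, 8, 10, 12 = 6.
- Without AE assessment: Weeks 2, 6, 10 = 3.
- 3/6 = 50%. Counting Day 0, where AE assessment is marked, gives 3/7 = 43%.

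**3. Infusions between AE questions**
- Dosing is every second, third or fourth day. As a check on the inputs, 12 weeks is 84 days; 84/4 = 21 and 84/2 = 42, which reproduces the protocol's range of 21 to 42 doses.
- As scheduled: 84/3 = 28 days between AE assessments. 28/4 = 7 infusions and 28/2 = 14 infusions.
- With AE assessment at all six visits: 84/6 = 14 days. 14/4 = 3.5 and 14/2 = 7 infusions.

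**4. What this means for SMC reviews**
- If biweekly means every two weeks, a given subject has a newly elicited AE record at every other review.
- This does not carry over to the committee's reviews as a whole, because they pool subjects. Suppose k subjects are in Segment 2 at once with independent, random enrolment timing (an assumption; the protocol gives no enrolment dates). The chance that a two-week window contains no AE-assessment visit from anyone is 0.5^k: 50% for k = 1, 25% for k = 2, 12.5% for k = 3 and about 3% for k = 5.
- If biweekly means twice a week, there are 24 reviews in 12 weeks. For one subject, 24 − 3 = 21 of them (87.5%) would follow no new scheduled AE assessment. The protocol does not say which meaning applies.

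**The case against.** The strongest reply is that safety information does not depend on these three visits. Subjects record AEs in a diary between visits, serious events go to the safety department within 24 hours of the investigator learning of them (Section 5.3.1), and the SMC discusses AEs continuously and reviews data as they arrive. This stands in part. These routes limit the consequence, but the 24-hour rule and the SMC discussion start only once someone knows of the event, and the diary review is itself unscheduled at these visits.

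A second reply is that the protocol often reserves the term study visit for the 4-weekly site visits. Section 3.1 contrasts study visits at Weeks 4, 8 and 12 with home-nurse sampling at Weeks 2, 6 and 10. Section 5.4 requires a pregnancy test at each study visit, and within Segment 2 after Day 0 Table 2 marks it only at Weeks 4, 8 and 12. On that usage the synopsis sentence on AE assessment at study-visit infusions agrees with Table 2, so it is not evidence of a contradiction. The reply does not reach Sections 5 and 5.2, which say visit without qualification, the word that Section 3.5.1.6 and footnote b use for Weeks 2, 6 and 10.

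A reader might infer that half of the SMC's Segment 2 reviews contain no newly elicited events. The documents do not support that: 3 of 6 is a per-subject visit count, and the reviews pool subjects. A reader might also infer that 4-week recall biases AE counts downward, or that events routinely reach the SMC four weeks late. The first is not quantified anywhere and overlooks the diary; the second is a worst case in which the subject contacts no one.

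Finally, the Introduction reports that by 14 December 2017 all 15 subjects had received at least 48 weeks of treatment. A schedule change can no longer alter any Segment 2 visit. That is correct, and it shifts the practical weight to reporting.

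**Conclusion.** The contradiction is real and confined to the protocol's own text: AE elicitation and diary review are required at each visit but not scheduled at three visits that the protocol calls visits. Per subject, scheduled AE elicitation occurs at 3 of 6 post-Day 0 Segment 2 visits, 28 days apart, across 7 to 14 infusions. If biweekly means every two weeks, the subject contributes no newly elicited AEs to every other SMC review. The count assumes visits on their nominal days (the Segment 2 window is ±1 day) and that staff follow the visit list; the documents do not show what was done in practice. It is a moderate point about the completeness and consistency of AE ascertainment. It does not show that SMC oversight failed or that AE counts are biased.

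**What to change.** Reconcile Sections 5, 5.2, 3.5.2.12 and 3.9 with Section 3.5.1.6 and Table 2 by adding AE assessment, concomitant medications and diary review to Section 3.5.1.6 and to the Week 2, 6 and 10 columns of Table 2. Section 5.2 gives the detailed diary review to the investigator, who may not be present at a home visit, so state that the nurse forwards the responses to the investigator for the next SMC listing. State in Section 3.7 what biweekly means. The cost is a few minutes per visit and three extra case report form pages per subject, with no new visit or staff.

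Because Segment 2 is finished for all 15 subjects, the study report should also say, alongside the Segment 2 AE counts, whether AEs were elicited and diaries reviewed at Weeks 2, 6 and 10, and whether this differed between sites or between home and site visits. This needs a check of source records and a short statement.

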3.8 Subject Identification

Subjects will be identified by their initials and a numerical code in the database. All subjects who sign the ICF/assent will receive a Subject Identification Number according to the following format: XX-YYY (site number-subject number) to be defined in a Study Manual. The anonymity of subjects will be maintained insofar as is required by law and to protect the subjects' rights to privacy. Personally identifying information may only be obtained by the investigator or their designee to complete the requirements of the protocol and must be kept by the investigator in strictest confidence and may not be released unless required by law. See Section 11 for additional information regarding confidentiality.

3.9 Treatment Compliance

The IMP will be provided by the sponsor and delivered to participating sites. IMP administration will be performed and recorded by study personnel or home nurse, or by subjects or their caregivers trained in self-administration.

Subjects will be given instructions how to document the receipt of IMP and how to return the used vials for accountability. The subjects will document IMP administration in the study diary. The study personnel will review the diary at each visit and document all doses used and missed in the CRF.

3.10 Protocol Deviations

Every effort should be made to avoid deviations from the protocol during the conduct of the trial. When protocol deviations do occur, the Investigator should promptly inform the Monitor, and the implications of each deviation must be reviewed and discussed. Any deviation must be documented, stating the reasons, date, actions taken, and the impact for the subject and/or trial for each deviation. This documentation must be kept in the Sponsor Files and Investigator Files. In case of any major protocol deviations (i.e., violations), the investigator and sponsor will decide on the further participation of the affected subject, after having discussed all relevant aspects. Such deviations will be reported to the IRB by the site according to its local IRB requirements. Deviations occurring outside of the study site, by vendors will be documented by the Sponsor and supplied to the site for IRB submission.

4 Restrictions

4.1 Concomitant and Prohibited Medications

The administration of concomitant medications, in accordance with the standard of care for subjects with hypoplasminogenemia, is permitted during the study. Any medications (e.g., prescription and non-prescription medications, blood products, herbal/natural products) taken by the subject within 30 days prior to Visit 1 (Screening) and/or during the course of the study will be recorded in the eCRF, including the dates of use, reason for use, dose, and dosage/schedule.

Any product containing plasminogen is not allowed from Screening to the end of the study.

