1.1.2 Current Treatment for Hypoplasminogenemia

There are 2 forms of plasminogen: Glu and Lys. Most literature references of plasminogen replacement therapy are based on the Lys form; it is important to note the Prometic plasminogen

is the Glu form, which has a longer half-life (approximately 2.5 days in healthy subjects) than Lys-plasminogen (0.8 days) (Collen *et al.*, 1991; Claeys *et al.*, 1973).

Attempted treatments for ligneous conjunctivitis lesions include: surgical removal; high dose intravenous corticosteroid treatment; topical treatment with heparin, corticosteroids and alpha-chymotrypsin, or cyclosporine; azathioprine; and hyaluronidase. These treatments are not consistently or completely successful in either the treatment or the prevention of lesion regrowth (Schuster *et al.*, 2007; DeCock *et al.*, 1995; Silva *et al.*, 2006; Rubin *et al.*, 1991). After treatment, including surgical removal, the lesions will usually recur. Local administration of fresh frozen plasma (which contains plasminogen) and other plasminogen-containing eye drops, however, has shown effectiveness in treating eye lesions of ligneous conjunctivitis (Heidemann *et al.*, 2003). Furthermore, continued topical administration of plasminogen-containing eye drops can treat the lesion and prevent regrowth. Other research shows that systemic administration of plasminogen concentrates results in partial resolution of the lesions (Schott *et al.*, 1998; Kraft *et al.*, 2000). A 6-month-old child treated with Lys-plasminogen preparation as a continuous infusion and later as daily bolus injections led to complete regression of ligneous conjunctivitis within 4 weeks and normalized hyperviscous secretions in the respiratory tract as well as skin wound healing (Schott *et al.*, 1998). Currently, there is no plasminogen replacement product approved for the treatment of plasminogen deficiency in the US.

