4.2 Other Restrictions

None.

5 Reporting of Adverse Events

Adverse events will be recorded from the first dose of IMP administration through 30 days after administration of IMP and collected by observation and reporting. AEs will be elicited from subjects by asking questions regarding changes in the subject's status at each visit.

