6.3.3 Efficacy Analysis

The primary endpoint is:

Overall Clinical Success in number and size of lesions or change in organ functionality at 48 weeks

The secondary efficacy endpoints are:

- Overall Clinical Success in number and size of lesions or change in organ functionality at 12 weeks
- CGI scores at 12 and 48 weeks
- Quality of life scores at 12 and 48 weeks

Overall clinical success is defined as 50% of subjects with visible or other measureable lesions achieving at least a 50% improvement in lesion number/size or functionality impact from baseline. Visible lesions are defined as lesions which can be imaged and analyzed with digital photography. Other measureable lesions are defined as lesions whose dimensions can be assessed by medical imaging studies (e.g. computed tomography, magnetic resonance imaging, ultrasound, etc) or functional assessments (e.g. spirometry, audiogram, oximetry, etc).

Clinical success will be further described as a graded evaluation of potential clinical responses; 1) Excellent response: $\geq 75\%$ decrease; 2) Good response: $\geq 50\%$ and $< 75\%$ reduction; 3) Moderate response: $\geq 25\%$ to $< 50\%$ reduction; 4) Minimal response: $< 25\%$ reduction; 5) No response: an increase or no reduction in the size of the lesion. Clinical responses will be determined by the principal investigator for the assessment of clinical success.

All efficacy results will be presented descriptively by individual subjects, including summarized hypoplasminogenemia symptoms over time recorded in subject diaries. The small sample size and high variability of disease presentation do not allow formal statistical analyses.

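### The primary lesion-response rule places no condition on other permitted or unexcluded lesion-directed treatment, so improvement from that treatment can count as response to plasminogen

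*Protocol*

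**What the plan says.** **Permitted treatment.** Protocol section 4.1 reads: "The administration of concomitant medications, in accordance with the standard of care for subjects with hypoplasminogenemia, is permitted during the study". The one ban is: "Any product containing plasminogen is not allowed from Screening to the end of the study". Medications taken during the study "will be recorded in the eCRF, including the dates of use, reason for use, dose, and dosage/schedule". Under "4.2 Other Restrictions" the protocol lists none.

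**Lesion-directed options.** Section 1.1.2 gives the background: "Attempted treatments for ligneous conjunctivitis lesions include: surgical removal; high dose intravenous corticosteroid treatment; topical treatment with heparin". Its list goes on to topical corticosteroids, cyclosporine, azathioprine and hyaluronidase. It describes these as neither consistently nor completely successful, and adds: "After treatment, including surgical removal, the lesions will usually recur".

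**Success rule.** Section 6.3.3 (and the synopsis in near-identical terms) states: "Overall clinical success is defined as 50% of subjects with visible or other measureable lesions achieving at least a 50% improvement in lesion number/size", or the same improvement in functional impact. Reductions are then graded. At least 75% is excellent, 50% to under 75% is good, and anything smaller falls below the success threshold. The principal investigator determines response.

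**Design.** Sections 3.4.1 and 3.4.2 say that the study is neither randomized nor blinded. Section 6.4 plans about 15 subjects without a formal calculation.

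**The concern.** The success rule compares a lesion at Week 12 or Week 48 with the same lesion at baseline and asks nothing about what happened in between. A subject could start or step up a permitted lesion-directed drug during the 48 weeks, or have a lesion removed surgically. If the lesion then measured at most half its baseline size, that subject would meet the definition exactly as written.

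A concurrent control arm would show how much improvement arises without the product. This trial has none, so whatever improvement is seen is read as the effect of plasminogen. The error can run in only one direction: an effective other treatment adds responders and never removes them. At stake is the interpretation of the primary efficacy endpoint of a study labelled pivotal.

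The secondary CGI-I scale gives no independent check. Its instruction in Appendix 15.3 asks for total improvement whether or not the drug caused it.

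**Working it through.** The protocol states no power, alpha, background response rate or number of subjects with measurable lesions, so there is no figure to reproduce. The check has two parts: reading the rules together, and an illustration on assumed inputs.

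**1. The rules side by side**

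| Question | Where | What the protocol fixes |
|---|---|---|
| Are lesion-directed drugs permitted? | 4.1 | Yes, if standard of care and free of plasminogen; no stable-dose or no-new-start condition |
| Is excision permitted? | 4.1, 4.2 | Not addressed; 4.1 speaks of medications, 4.2 restricts nothing |
| Does the success rule exclude lesions treated by other means? | 6.3.3 | No |
| Does the missing-data rule cover them? | 6.2 | No; it concerns missing values only |
| Are such treatments recorded? | 4.1, 3.5.2.3, Table 2 | Medications yes; surgery is named only as history before screening, and Table 2 has no row for on-study procedures |

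Applied literally, a subject with one baseline lesion that is excised and does not regrow has a reduction of 1/1 = 100%, graded excellent. If one of two lesions is excised, the reduction in number is 1/2 = 50%, which meets the threshold.

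**2. What one subject is worth (assumed counts)**

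Let n be the number of subjects with measurable lesions. The weight of one subject is 100/n percentage points:

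- n = 8: 100/8 = 12.5 points
- n = 10: 100/10 = 10 points
- n = 15 (every enrolled subject): 100/15 = 6.7 points

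With n = 10, two subjects counted because of other treatment turn 3/10 = 30% (fail) into 5/10 = 50% (success).

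**3. Chance of meeting the rule (assumed counts and response rate)**

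Read the bar as at least half, so r = n/2 rounded up. Suppose m subjects count as responders because of other treatment, and each of the rest responds to plasminogen with probability p. Then

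P(success) = P(X ≥ r − m), with X ~ Binomial(n − m, p).

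For p = 0.30:

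| n | r | m = 0 | m = 1 | m = 2 | m = 3 |
|---|---|---|---|---|---|
| 8 | 4 | 0.194 | 0.353 | 0.580 | 0.832 |
| 10 | 5 | 0.150 | 0.270 | 0.448 | 0.671 |
| 15 | 8 | 0.050 | 0.093 | 0.165 | 0.276 |

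For example, n = 10 and m = 2 gives P(X ≥ 3) with X ~ Binomial(8, 0.30) = 0.448. The value p = 0.30 was chosen to show a product that should miss the bar. It is not an estimate of this product's effect.

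**The case against.** The case on the other side has real substance.

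- **The main confounders are already barred.** The local treatments that section 1.1.2 credits with effectiveness are fresh frozen plasma and plasminogen-containing eye drops. Section 4.1 bans them during the study, and exclusion criterion 7 bars their use within 2 weeks of screening. The remaining treatments are called inconsistent, with recurrence usual. This limits lasting bias, but does not remove it for a treatment given shortly before the Week 12 or Week 48 assessment.
- **This could be left to the SAP.** Handling of intercurrent treatment often sits there. Here, however, the protocol itself fixes the success rule. A SAP that counted such subjects as non-responders would be changing that rule.
- **Counting improvement whatever else was given is a recognised strategy.** That is so, but without a control arm it cannot isolate the product's effect, and the protocol does not say that it chose this strategy.
- **Results are shown by subject, with medication dates and reasons recorded.** A reader could match drug use to response. That helps for drugs, less clearly for procedures, and does not alter the success count.
- **Interim results look far from the bar.** The introduction reports 13 of 14 visible lesions resolved at 12 weeks and the last too small to measure. These are lesions rather than subjects, and the report is silent on other treatment, but a result close to 50% looks unlikely.

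A reader might infer that the protocol allows excision. It does not say so: the permission in section 4.1 covers medications, and section 1.1.2 lists surgical removal only as an attempted treatment. A reader might also infer that any shrinkage counts as success. It does not: improvement below 50% is not success under section 6.3.3.

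**Conclusion.** The point stands as a gap in the primary efficacy definition. Standard-of-care medication other than plasminogen-containing products is permitted, excision is not excluded, and the success rule is indifferent to both. An improvement of at least 50% brought about by such treatment can therefore be counted as response to plasminogen.

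The size of the bias is unknown. Each affected subject would be worth 10 percentage points if 10 subjects have measurable lesions, with a range of 6.7 to 12.5 points for 15 down to 8. These counts, the 30% response rate and the number of affected subjects are all assumptions.

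It would go too far to conclude that other treatments' effects have been credited to plasminogen, or that a reported success would be false. The protocol documents no such use, and the interim lesion results give no sign of a result near the bar. The matter deserves correction because attribution in a single-arm pivotal study rests entirely on this definition and the correction is cheap.

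**What to change.** Change the analysis only; nothing here concerns which treatments subjects may receive.

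1. Add to section 6.3.3, and to the matching synopsis text: a subject whose baseline lesion was excised, or who started or intensified other lesion-directed treatment after the first dose, counts as a non-responder at all later assessments (Weeks 12 and 48).
2. Report the protocol-defined result on observed values beside it, so that the effect of the rule is visible.
3. Confirm that on-study procedures are captured in source documents or the eCRF, since section 4.1 requires only medications to be recorded.
4. Date the change as made after the interim results and before database lock, by which time section 6.3 requires the SAP to be final. The introduction says that all 15 subjects had at least 48 weeks of treatment by 14 December 2017, so also state whether Week 48 results had been seen.

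**Cost.** One sentence in the definition, one further table and a check of procedure records. The success rate may be slightly lower. The rule is also added after interim data are known, which is why both results should be shown.
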